Physical functioning in this clinical context can be measured using a specific quality of life scale in upper limb lymphoedema, together with the FACT-B+4 Health Survey Questionnaire. Sentinel lymph node biopsy staging reduces the need for axillary node clearance (ANC), but 30% of breast cancer patients are node positive and require ANC to remove diseased nodes.^{116,17,191} A clinical endpoint of >10% increase in ipsilateral arm volume (versus contralateral arm) is an accepted criteria for a diagnosis of lymphoedema.^{8,20,21,22} Up to 40% of women develop lymphoedema by 18 months post ANC.¹⁹¹ Intervention before arm swelling becomes chronic may prevent the complications of lymphoedema after ANC.

In women undergoing axillary node clearance for node positive breast cancer in the ALMANAC Trial, 40% developed arm volume increases >10% (compared to baseline and contralateral arm) by 18 months post-surgery.

Arm measurements are not routine practice prior to axillary clearance but our data from an ongoing prospective study and the ALMANAC Trial¹⁹¹ data prospectively collected indicates that 40- 45% of patients develop arm volume increases between 4-8% by 3 or 6 months after surgery and 5% already have a 10% increase (i.e. Lymphoedema). The 45% of women with arm volume increases between 4-8% at 3 or 6 months post clearance account for the majority (50-60%) of patients who subsequently develop lymphoedema.²³¹ Counter-intuitively the absolute level of increase between 4 and 9% does not clearly define risk of later lymphoedema because despite no compression sleeve application up to 40% of women do not progress to develop lymphoedema by 2 years.

Conventional advice is that early arm swelling at 3 months does not portend chronic swelling and should be treated conservatively.²⁴ In the ALMANAC Trial¹⁹¹ prospective arm measurements identified early arm swelling (4-5%) in patients and predicted 53% of cases would subsequently develop lymphoedema (arm swelling 10%) by 18 months, whereas for 6% arm swelling, the specificity for subsequent lymphoedema was 80% (sensitivity 56%) and this degree of arm swelling at 3 or 6 months predicted 60% of lymphoedema cases at 18 months follow-up. Arm swelling of 4-8% is usually not clinically apparent unless arm measurements have been made preoperatively and only 3% of women in the axillary clearance arm of the ALMANAC Trial complained of significant swelling at 6 months^{19,251}

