2.0 TRIAL DESIGN

1100 women undergoing ANC for breast cancer in 9 centres across the UK will be approached to undergo baseline (pre-operative) and subsequent BEA monitoring, along with perometer arm measurements (see flow diagram). A comparison of the sensitivity and specificity of BEA versus perometer measurement will be made firstly in women who develop arm swelling >10% by 6 months (estimated at 231/1100 (21%) of the initial group). Percentages are estimated from ALMANAC Trial (see Annex 4d). Secondly women with an arm volume increase 4-8.9% at 1, 3, 6 months where effectively the BEA 6 months readings will be compared with final 18 month perometer scores to assess the prediction of lymphoedema at 18 months by BEA. Thirdly, women with a <4% Perometer arm volume increase up to 6 months (estimated n=363/1100 with estimated lymphoedema at 18 months of 46 (14% of 264)) will be used to determine the sensitivity and

specificity of BEA 6 month measures compared to the perometer 6 month measurement in predicting the 18 month outcome.

We originally estimated we would need to screen over 1000 patients to enrol sufficient women into the PLACE Trial using perometer measurements, we will determine if BEA has a >80% sensitive and a >80% specific accuracy and currently the specificity of arm swelling measured by perometer is 87% specific for subsequent lymphoedema at 18 months with a sensitivity of 54% (assessed from ALMANAC trial data). We will recruit 1100 women before ANC into the five year study to allow for 10% drop-out over the course of the study.

The Perometer sensitivity is reported as 85% +/-3.6% (95% CI 81.4% to 88.6%) and we will be able to detect a greater or equal to 7% improvement in sensitivity with BEA to 92+/-2.5% (95%CI: 89.5-94.5%) and the Perometer specificity is 55% +1-4.1% (95% CI 50.9% to 59.1%) thus we will be able to detect a >9% improvement in specificity with BEA to 64%+/-3.9% (95%CI:60.1 to 67.9%) with this sample size, since the confidence intervals do not overlap.

Gold standard at 18 months	Test P+	Test P-	Total
	+168[contact]
	-168[contact]
Total	336[contact]

sensitivity = 307/352 = 87%
 specificity = 284/523 = 54%

Arm volume measurement at 1 month will not be used to implement treatment outside of the trial. In women who develop lymphoedema >10% at 3 months, sleeves will be applied and the 3 month BEA value compared to the perometer used in the analysis. For all others, the 6 month value will be used.

[figure not shown]

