5 STATISTICAL ANALYSIS

Analysis 1 and 2 will directly compare BEA and perometer assessment at a given time point (6 and 18 months). The reported concordance/correlation in small series is 0.93¹³⁴¹. Thus, even if a sleeve has been applied in patients before 6 months' measurements and the arm circumference has been reduced, the reduction in fluid in the arm should have reduced both the perometer and BEA scores concomitantly.

Sample Size Calculation

We estimate 1100 women are needed for screening by perometer to recruit 270 women to the PLACE trial and this sample size of 1100 (derived from having approached 1500 women to take part in the study) allows us to assess equivalence for sensitivity and specificity for BEA compared to perometer measurement with tight confidence intervals. Previous reported correlation between the techniques is very high¹¹⁵, and this sample size allows us to have a 95% Confidence Interval (CI) around our sensitivity and specificity estimates such that they are $\pm 5\%$ or less. Thus if perometer and BEA are equivalent in sensitivity and specificity to within 5% of each other, we would expect that the BEA would become the preferred option as it would be mobile, non-invasive and simpler to use in any outpatient setting compared to a fixed, large instrument, such as the perometer. There will be less patients with lymphoedema at 6 months but nonetheless if BEA sensitivity is 95% of the perometer sensitivity, we can demonstrate this with a 95% CI of 91.42% to 97.49%. If the BEA sensitivity rate was as low as 90%, we would have a 95% CI of 85.12% to 93.49%. All subsequent analyses will use sample sizes based on larger numbers as there will be more lymphoedema events at 18 months and again at 36 months but their confidence intervals are within $\pm 5\%$. We have used the exact method for calculating confidence intervals for a binomial proportion (Documenta Geigy Scientific tables page 185 equation 769); the actual calculation was done using the www.measuringusability.com/wald.htm website calculator.

The sample will allow us to measure accurately, inter- and intra-technique variability at different time points.

Analyses 1 to 3 will assess whether BEA can be used instead of perometer in defining lymphoedema status. The second group of analyses is to look for any variables collected at operation or in the first 6 months post operation that singly or in combination can be used to predict lymphoedema status at or beyond 18 months.

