Analysis 1

Sensitivity and specificity analysis of the BEA assessment (lymphoedema or not) against the 'gold standard' perometer assessment (lymphoedema or not) using data available by 6 months.

Analysis 2

Analysis of the sensitivity and specificity of the 18 month BEA assessment status (lymphoedema or not) against the 'gold standard' 18 month perometer assessment status (lymphoedema or not) using all data available at 18 months.

Analysis 3

Assessment of the relationship between perometer measurement and BEA measurement.

Analysis 4

Cox regression multivariate analysis of the time to Lymphoedema (as defined by perometer) to find out which combination of variables gives the best prediction of this complication.

Analysis details:

Analysis 1: Sensitivity and specificity analysis of the BEA assessment (lymphoedema or not) against the 'gold standard' perometer assessment (lymphoedema or not) using data available by 6 months. Can BEA be used instead of perometer in predicting lymphoedema status?

All cases with a 6 month BEA and perometer measurement will be used. This is acceptable even if some cases are treated as what we are asking is do cases measured at the same time (and therefore under the same circumstances whatever they are) agree in their assessment of lymphoedema status.

The two methods will not agree on their actual scores as perometer measurements are in percentage differences and BEA measures are ratios. However we will assess the relationship between all the pairs of values using statistical techniques recommended by Bland and Altman for assessing agreement between methods of measurements with multiple observations per individual^{36,311} (see also analysis 3).

With 1100 cases consented to having measurements taken and followed-up, we would expect 231 to have developed lymphoedema (positive) using perometer assessment and 869 to be negative at 6 months. If we accept that BEA status has at least 95% sensitivity and 95% specificity against the perometer status then the 95% CI for sensitivity based on 231 cases is 91.42% to 97.49% and for specificity based on 869 cases is 93.31% to 96.47% (CI's calculated by 'exact' method). Consequently if sensitivity is <91 % or specificity is <93% we can conclude that the true BEA rates are not as high as 95%. This analysis can be done 6 months after the last case has their 6 months measurements taken. The perometer is deemed to be the gold standard.

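### Two unreconciled early lymphoedema rates, 5% and 21%, lie behind the 6-month sensitivity precision of Analysis 1, which holds only near the higher one

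*Protocol*

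**What the plan says.** - **Section 1.4**, citing "our data from an ongoing prospective study and the ALMANAC Trial", describes early arm swelling "by 3 or 6 months after surgery and 5% already have a 10% increase (i.e. Lymphoedema".
- **Section 2.0** sizes the first comparison on "women who develop arm swelling >10% by 6 months (estimated at 231/1100 (21%) of the initial group). Percentages are estimated from ALMANAC Trial", with a reference to an Annex 4d that is not in the document.
- **Section 5, Analysis 1** carries this forward: "With 1100 cases consented to having measurements taken and followed-up, we would expect 231 to have developed lymphoedema (positive) using perometer assessment". The remaining 869 are taken as negative. Group C later in Section 5 has about 210 women, which is 21% of 1000.
- **Section 5, Sample Size Calculation** promises 95% intervals for sensitivity and specificity within 5 points either way. It concedes fewer cases at 6 months, but supports the claim with intervals of 91.42% to 97.49% (at 95% sensitivity) and 85.12% to 93.49% (at 90%).
- **Section 5, Analysis 1** derives a decision limit from the first interval: an observed sensitivity under 91% is to be read as showing that the true rate is below 95%.
- **Section 2.0**, for women whose increase stays under 4% to 6 months, gives "estimated n=363/1100 with estimated lymphoedema at 18 months of 46 (14% of 264".

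**The concern.** The two rates use essentially the same perometer threshold and the same early window, and both lean on the same earlier trial, yet they differ about four-fold. The number of perometer-positive women alone determines how precisely 6-month sensitivity can be estimated. The plan intends to act on that precision: it says bioimpedance would become the preferred method if the two agreed to within 5 points. If the true rate is well below 21%, neither the stated precision nor the 91% limit follows at 6 months.

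**Working it through.** **Inputs.** N = 1100; rates of 21% (Sections 2.0 and 5) and 5% (Section 1.4); exact (Clopper-Pearson) two-sided 95% intervals, the method named in Section 5; illustrative sensitivities of 95% and 90%, as in Section 5.

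**1. Reproducing the plan's figures.**
- 0.21 × 1100 = 231.
- 219/231 gives 91.10–97.29 and 220/231 gives 91.64–97.60, against the printed 91.42–97.49.
- 208/231 gives 85.44–93.58, against the printed 85.12–93.49.

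The printed intervals are met to within about 0.3 points. The arithmetic from 21% is sound; only the input rate is in question.

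**2. The same calculation at other rates.** Half-width = (upper limit − lower limit)/2.

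| Rate | Positives | Near 95% sensitivity | Half-width | Near 90% sensitivity | Half-width |
|---|---|---|---|---|---|
| 21% | 231 | 219/231: 91.1–97.3 | 3.1 | 208/231: 85.4–93.6 | 4.1 |
| 15% | 165 | 157/165: 90.7–97.9 | 3.6 | 148/165: 84.0–93.9 | 4.9 |
| 10% | 110 | 104/110: 88.5–98.0 | 4.7 | 99/110: 82.8–94.9 | 6.1 |
| 5% | 55 | 52/55: 84.9–98.9 | 7.0 | 50/55: 80.1–97.0 | 8.5 |

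A half-width of 5 points or less needs at least 94 positives (8.5% of 1100) at 95% sensitivity and at least 158 (14.4%) at 90%.

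**3. The 91% decision limit.** Suppose the true sensitivity is 95%. The rule fires when the observed count is below 0.91 × n.
- n = 231: 0.91 × 231 = 210.2, so it fires at 210 or fewer. P(X ≤ 210 | 231, 0.95) = 0.006.
- n = 55: 0.91 × 55 = 50.05, so it fires at 50 or fewer. P(X ≤ 50 | 55, 0.95) = 0.140.

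At 50/55 = 90.9% the rule fires, although the exact interval (80.1–97.0) still contains 95%.

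**4. What does not move.**
- 6-month specificity: at 5% there are 1100 − 55 = 1045 negatives, and 993/1045 gives 93.5–96.3.
- Analysis 2 starts from 350 positives and 650 negatives at 18 months. Its intervals reproduce exactly (333/350: 92.34–97.15; 618/650: 93.12–96.61).

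**5. The under-4% stratum (Section 2.0).**
- 0.14 × 264 = 37.
- 0.14 × 363 = 51, where 363 is the stratum size stated in the same sentence (33% of 1100).
- 0.14 × 330 = 46, where 330 is Group A in Section 5 (33% of 1000).

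The printed 46 therefore matches neither denominator in its own sentence. For scale, at an assumed sensitivity of about 80%, 37/46 gives 66.1–90.6.

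**The case against.** A reader might go further and infer that 5% is the right rate, so that the 6-month precision is simply wrong. The documents do not support that.

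- **The cohort split fits 21%.** Groups A, B and C in Section 5 are 33% + 46% + 21% = 100%. With 5% in Group C the sum is 84%, and 16% of women belong to no group.
- **The majority statement does not favour 5%.** Section 1.4 says women with early moderate swelling make up 50–60% of those who develop lymphoedema later, so women already above 10% are outside that denominator. If early cases stay positive, 21% gives (350 − 210 − 46)/(350 − 210) = 94/140 = 67%, and 5% gives (350 − 50 − 46)/(350 − 50) = 254/300 = 85%. The 21% figure is the closer of the two.
- **A distributional argument cannot decide it.** Section 7 gives a 6-month mean increase of 5.14% but no standard deviation or shape, so any tail proportion derived from it is assumed.
- **The sources differ.** The 5% pools the sponsor's ongoing study with the earlier trial and may partly be a 3-month figure. The 21% is attributed to the earlier trial alone.

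Three further criticisms are tempting but do not stand.

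- **Drop-out.** The 231 appears to ignore the 10% allowance, but the printed limits already largely match a base of 1000: 751/790 gives exactly 93.31–96.47, and 200/210 and 189/210 give the printed lower limits 91.42 and 85.12.
- **The 80% target.** In Section 2.0 this concerns prediction of 18-month status, not the same-time agreement of Analysis 1.
- **Larger later samples.** The statement "All subsequent analyses will use sample sizes based on larger numbers" sits with the numbered analyses at 18 and 36 months, so the small under-4% stratum does not contradict it.

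What stands of the defence is that the documents do not establish which rate is right, and that the consequence is confined to one interval and one limit of a secondary comparison. What it does not remove is the conflict itself. Both rates are printed in the protocol, and so is the precision claim that depends on the choice between them.

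**Conclusion.** The point holds as an unreconciled conflict in an input, not as proof that the sample size is wrong. The 6-month sensitivity claim is conditional on a rate near 21%. The half-width is about 3 to 4 points with 231 positives and about 7 to 8.5 points with 55, and the chance that the 91% limit wrongly rejects a true 95% sensitivity rises from 0.6% to about 14%. These figures assume 1100 women measured, exact intervals and the plan's own illustrative sensitivities. At intermediate rates the claim fails first at 90% sensitivity (below about 14%) and then at 95% (below about 8.5%). The stratum count in Section 2.0 is a separate, smaller error that holds whichever rate is right. The primary endpoint is incidence at 2 and 5 years, and the 1100 is also justified as the screening number for PLACE; neither depends on this. It should be fixed, but it does not threaten the trial.

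**What to change.** 1. Check the 5% and the 21% against the source data. State for each its population, time window and threshold, and keep one rate for planning or explain why both are true.
2. Restate the Analysis 1 sensitivity interval and its decision limit for the reconciled number of positives. If the rate stays uncertain, show both ends (55 and 231) and replace the blanket 5-point claim with the actual half-widths.
3. If the rate is near 5%, rest the sensitivity conclusion on the 18-month analysis (about 350 positives) and label the 6-month sensitivity descriptive.
4. Correct the under-4% stratum in Section 2.0 so that its size, percentage and event count agree, and state its precision.

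The cost is restated text and possibly a weaker 6-month claim. No added patients, visits or measurements are needed.

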A further assessment of the BEA value cut off level will be made to see if a change in the standard definition is worth recommending (ROC analysis). This will be done at 18m from the start of the study (using cases accrued in the first year) and repeated on the new cases post 1 year recruitment to see if a new cut off level works on the second data group. The final sensitivity and specificity analysis will take place 6 months after the last case is recruited.

Analysis 2: Analysis of the sensitivity and specificity of the 18 month BEA assessment status (lymphoedema or not) against the 'gold standard' 18 month perometer assessment status (lymphoedema or not) using all data available at 18 months.

This analysis uses all the data available at 18 months, following the same logic and procedures as Analysis 1. Assuming at least 1,000 women are followed-up to 18 months after surgery, there will be more lymphoedema cases, this is estimated to be 35% of the total group (i.e. 350 cases). The sensitivity calculations produce a 95% CI for a 95% BEA sensitivity rate (333/350) against the perometer status at 18 months of 92.34 to 97.15 (again using the 'exact' method). The other 650 cases are used for the specificity calculation, here the 95% CI for 95% BEA specificity (618/650) has a 95% CI of 93.12 to 96.61. Consequently if sensitivity is <92% or specificity is <93% we can conclude that the true BEA rates are not as high as 95%.

Analysis 3: Assessment of the relationship between perometer measurement and BEA measurement. Any changes will be measured by both systems at different time points (1m, 3m, 6m, 12m and 18m and later on out to 5 years) and all results will be used as the modelling will be based on the paired perometer and BEA values. This will be used to define the relationship between the two methods (we will use Bland-Altman methods^{136,371} at individual time points and generalized estimating equations (GEE) regression models across time points). The relationship established may lead to a clearer definition of 'true' lymphoedema status when using either system.

Analysis 4: Cox regression multivariate analysis of the time to Lymphoedema (as defined by perometer) to find out what combination of variables gives the best prediction of these events.

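### The percentage lines for concluding that BEA falls short of 95% are stricter than the exact 95% CI they are said to follow from, and hold only for the assumed denominators

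*Protocol*

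**What the plan says.** Section 5 of the protocol treats perometer status as the gold standard and 95% as the reference rate for BEA. Analysis 1 (6 months) begins: "If we accept that BEA status has at least 95% sensitivity and 95% specificity against the perometer status". It then gives the expected precision: "the 95% CI for sensitivity based on 231 cases is 91.42% to 97.49" (per cent), and "for specificity based on 869 cases is 93.31% to 96.47% (CI's calculated by 'exact' method". From these intervals it concludes: "Consequently if sensitivity is <91 % or specificity is <93% we can conclude that the true BEA rates are not as high as 95" (per cent).

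Analysis 2 (18 months) follows the same logic with 350 positives and 650 negatives. It gives a "95% BEA sensitivity rate (333/350) against the perometer status at 18 months of 92.34 to 97.15" and says "the 95% CI for 95% BEA specificity (618/650) has a 95% CI of 93.12 to 96.61". Its conclusion is: "Consequently if sensitivity is <92% or specificity is <93% we can conclude that the true BEA rates are not as high as 95" (per cent).

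The sample size text in the same section names the exact binomial method. No significance level other than that of the 95% intervals is attached to these lines.

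**The concern.** An interval around an *observed* 95% shows how precise the estimate would be if BEA performed at 95%. Its lower limit is not the critical value for rejecting a *true* 95%. The rule that corresponds to a 95% CI is to conclude that BEA is below 95% when the upper limit of the interval around the observed rate lies below 95%. The protocol uses the lower limit of the other interval and also rounds it down to a whole percent.

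At the planned numbers both steps push the line towards leniency for the new device. Some results whose own reported CI excludes 95% would not cross the line, and a real shortfall would be found less often. A fixed percentage also carries its error rate only at the denominator for which it was worked out, and the number of positives at 6 months is an estimate.

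**Working it through.** **Inputs (protocol, Section 5).** Reference rate 95%; n = 231 and 869 (Analysis 1), 350 and 650 (Analysis 2); lines 91%, 93%, 92% and 93%; exact (Clopper-Pearson) two-sided 95% intervals.

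**Formulas.** The exact limits for x/n are the 2.5% quantile of Beta(x, n−x+1) and the 97.5% quantile of Beta(x+1, n−x). The one-sided error of a rule that rejects at k or fewer is P(X ≤ k) for X ~ Binomial(n, 0.95). The chance of detecting a true rate p is the same sum with p in place of 0.95.

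**Step 1: the protocol's intervals.** Analysis 2 reproduces exactly: 333/350 gives 92.34–97.15% and 618/650 gives 93.12–96.61%. Analysis 1 reproduces only approximately from the stated n: 219/231 gives 91.10–97.29%, 220/231 gives 91.64–97.60%, 825/869 gives 93.26–96.30% and 826/869 gives 93.39–96.40%. Every lower limit still rounds down to the printed line, so what follows does not depend on this.

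**Step 2: the largest count that rejects, and its error at a true 95%.** For the first row, 0.91 × 231 = 210.21, so the printed line rejects at 210 or fewer. The unrounded limit gives 0.9142 × 231 = 211.18, so 211 or fewer. The exact CI has upper limit 94.98% at 212 and 95.32% at 213, so it rejects at 212 or fewer.

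| n | Printed line | Unrounded limit | Upper CI limit < 95% | Line silent, CI excludes 95% |
|---|---|---|---|---|
| 231 | <91%: 210 (0.64%) | 91.42%: 211 (1.27%) | 212 (2.39%) | 211–212 |
| 869 | <93%: 808 (0.56%) | 93.31%: 810 (1.22%) | 812 (2.46%) | 809–812 |
| 350 | <92%: 321 (0.59%) | 92.34%: 323 (1.82%) | 323 (1.82%) | 322–323 |
| 650 | <93%: 604 (1.26%) | 93.12%: 605 (1.90%) | 605 (1.90%) | 605 |

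Example: 211/231 = 91.3% has an exact 95% CI of 86.95–94.63%. The interval excludes 95%, but the rate is not below 91%.

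**Step 3: where the mismatch comes from.** In Analysis 2 the unrounded limits give the same decisions as the CI, so rounding explains all of it. In Analysis 1, 212/231 and 811–812/869 still disagree after the rounding is undone. That remainder comes from using the lower limit around an observed 95% as a critical value.

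**Step 4: chance of concluding that BEA is below 95%.**

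| True rate | Printed line | Unrounded limit | Upper-limit rule |
|---|---|---|---|
| 6-month sensitivity 90% (n = 231) | 71% | 78% | 84% |
| 6-month specificity 93% (n = 869) | 51% | 62% | 71% |
| 18-month sensitivity 91% (n = 350) | 71% | 82% | 82% |

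**Step 5: fewer positives than planned (assumed).** The protocol expects 231 positives by 6 months (21% of 1100). Its Introduction also reports that 5% of women in earlier data already had a 10% increase at 3 or 6 months; 5% of 1100 is 55. I take 100 and 55 as illustrations.

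- n = 100: <91% rejects at 90 or fewer, error 2.8%. The exact CI of 90/100 is 82.38–95.10%, which includes 95%.
- n = 55: <91% rejects at 50 or fewer, error 14.0%. The exact CI of 50/55 is 80.05–96.98%, which includes 95%.

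**Step 6: either criterion in Analysis 1.** Positives and negatives are separate women, so at a true 95% for both the chance that at least one criterion rejects is 1 − (1−0.0064)(1−0.0056) = 1.2% with the printed lines, and 1 − (1−0.0239)(1−0.0246) = 4.8% with the upper-limit rule.

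**The case against.** **The sentences are true as written.** At the planned denominators every result below a line has an exact CI that excludes 95%: the upper limits at 210/231, 808/869, 321/350 and 604/650 are 94.28%, 94.59%, 94.38% and 94.77%. The lines are a sufficient condition, and neither sentence says what follows when a line is not crossed. This stands. A reader might infer that the line and the CI decide borderline results in opposite ways, or contradict each other. The text does not support that: in those bands the line says nothing and the CI speaks.

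**Much of it is rounding.** This also stands. A reader might infer that all four lines fail because the wrong quantity is inverted. In Analysis 2 the unrounded limits agree with the CI throughout, and even 211/231 (91.34%) would cross an unrounded 91.42%. The power losses from the printed lines therefore mix the two causes.

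**No level is stated, and two criteria are joined by *or*, so caution is defensible.** In part. The 2.5% yardstick is inferred from the two-sided 95% intervals. But the lines are presented as consequences of those intervals, and nothing suggests that a stricter level was intended.

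**Little hangs on it.** Comparison with the perometer is a secondary objective, treatment decisions rest on the perometer, and the published CI would show the result anyway. That limits the weight of the point. It does not make the stated lines follow from the stated intervals.

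**Conclusion.** The point holds in a limited form. At 231, 869, 350 and 650 the lines are valid but conservative: one-sided errors of 0.56% to 1.26% against at most 2.5%, and bands of 2, 4, 2 and 1 counts in which the protocol's own exact CI excludes 95% and the line is silent. Rounding accounts for all of this in Analysis 2 and for part of it in Analysis 1. The power lost, for example 84% to 71% for a true 6-month sensitivity of 90%, is the joint effect of rounding and inversion.

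The conservatism is not guaranteed. It depends on the planned denominators, and with clearly fewer positives the 91% line can reject where the CI includes 95%. The 2.8% and 14% rest on assumed counts of 100 and 55 and are not forecasts. This is a minor point. It touches neither the primary endpoint nor the sample size.

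**What to change.** Replace both sentences in Section 5 with: *we will conclude that the true BEA rate is below 95% if the upper limit of the exact two-sided 95% CI for the observed rate is below 95%*, applied to the realised denominators. Numeric lines, if kept, should be labelled as illustrations for the planned numbers: 212/231, 812/869, 323/350 and 605/650 or fewer.

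The cost is two sentences, with no extra patients or data. BEA would face a slightly stricter line at the planned numbers, and the either-criterion false-conclusion rate in Analysis 1 would rise from about 1.2% to 4.8%. That figure covers Analysis 1 alone, not both analyses together.

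### Analysis 2 scores status at the 18-month visit, but its 350 positives and fixed 92% line make no allowance for women treated earlier who may no longer read above 10%, or may be excluded

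*Protocol*

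**What the plan says.** Section 5, Analysis 2 compares "the 18 month BEA assessment status (lymphoedema or not) against the 'gold standard' 18 month perometer assessment status (lymphoedema or not") and follows the logic of Analysis 1. That logic is to judge agreement between two readings taken on the same occasion, and it accepts treated cases.

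The planning figures are:

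- **Denominator.** "Assuming at least 1,000 women are followed-up to 18 months after surgery", lymphoedema cases are put at 35%: "this is estimated to be 35% of the total group (i.e. 350 cases").
- **Precision.** The plan gives a "95% CI for a 95% BEA sensitivity rate (333/350) against the perometer status at 18 months of 92.34 to 97.15".
- **Decision rule.** "Consequently if sensitivity is <92% or specificity is <93% we can conclude that the true BEA rates are not as high as 95"%.

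The Sample Size Calculation in the same section adds that "All subsequent analyses will use sample sizes based on larger numbers as there will be more lymphoedema events at 18 months".

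On treatment:

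- Section 3.4 starts lymphoedema treatment once the increase exceeds 10% on two occasions.
- The opening of section 5 says of a sleeve that "the reduction in fluid in the arm should have reduced both the perometer and BEA scores concomitantly".
- The text on Groups A to C, after Analysis 4, puts about 210 women above 10% by 6 months. It also says that none of the analyses described will use cases treated before 6 months.

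**The concern.** A same-visit comparison takes as its positives the women whose perometer reading exceeds 10% at that visit. The 350 appears to count something else. Analysis 1 states its 6-month figure as "we would expect 231 to have developed lymphoedema (positive) using perometer assessment", and the sample-size text then has events rising at 18 and again at 36 months. A cumulative count must rise in that way. The number of women above 10% at a visit need not, particularly when those found above 10% are treated and the protocol itself expects treatment to lower the reading.

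Two statements rest on about 350 positives: the quoted interval, and the 92% line for concluding that BEA is not 95% sensitive. If the real denominator is much smaller, the interval is wider. A fixed line at 92% would then reject a BEA whose true sensitivity is 95% more often than the 2.5% implied by the upper limit of a two-sided 95% interval.

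**Working it through.** **1. Reproduce the plan.** The exact (Clopper-Pearson) 95% interval for x positives out of n has lower limit Beta(0.025; x, n−x+1) and upper limit Beta(0.975; x+1, n−x).

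- 333/350 gives 92.34% to 97.15%.
- 618/650 gives 93.12% to 96.61%.

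Both match the protocol to two decimals. The arithmetic is right, so the question is the input n = 350.

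**2. Share of the 350 exposed to early treatment.** The Group A to C counts are 330, 460 and 210, which sum to 1,000, so they are on the same base as the 350. Women above 10% by 6 months make up 210/350 = 60% of the cases, before counting those found between 6 and 18 months.

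**3. Test the 92% line.** For each n, take the largest count x with x/n below 92%. The rule is valid if the exact upper limit for x/n is below 95%. The false-rejection chance is P(X ≤ x) for X ~ Binomial(n, 0.95). The n below 350 are assumed values, because the documents give no share of treated women who read 10% or less.

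| n | Exact 95% CI at about 95% observed | Largest count below 92% | Upper limit there | P(observed <92%, true 95%) |
|---|---|---|---|---|
| 350 (plan) | 92.34–97.15 (333/350) | 321 | 94.38 | 0.6% |
| 300 | 91.89–97.17 (285/300) | 275 | 94.53 | 0.9% |
| 280 | 91.75–97.24 (266/280) | 257 | 94.72 | 1.4% |
| 210 | 91.42–97.69 (200/210) | 193 | 95.21 | 3.6% |
| 140 | 89.97–97.97 (133/140) | 128 | 95.49 | 4.9% |

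Checking every n shows that the rule holds throughout 250 to 350 and first fails at 249. Because counts are whole numbers, it then holds at some values (for example 231, upper limit 94.98%) and fails at others down to 202. It holds at 200 and 201, and fails at every n from 50 to 199.

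**4. What loss is needed?** Falling to 249 means losing 101 of 350 women, or 29%. If only the 210 early cases could revert, that is 101/210 = 48% of them. The 18-month denominator falls below the 231 planned for 6 months only if at least 120 of 350 (34%) are lost.

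**5. The exclusion statement.** If all 210 early cases were removed, 350 − 210 = 140 would remain. The lower arm of the interval is then 95.00 − 89.97 = 5.03 points, against the ±5% in the Sample Size Calculation. This is a bound, since not all 210 would be treated before 6 months.

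**6. Specificity.** Women who revert join the negatives. With 720 negatives the exact interval at 95% is 93.14% to 96.47%, no worse than stated.

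**The case against.** The strongest reply is that the premise is not proven. The protocol never labels the 35% as cumulative. The table in section 2.0, drawn from the earlier axillary surgery trial, is headed as the gold standard at 18 months and has 352 positives out of 875 (40%), so the 35% could already reflect 18-month readings. This stands, and it is why the point asks the sponsor to say which quantity is meant. It does not dispose of the concern, because nothing in the document shows that women in that earlier trial were treated on passing 10%, as they are here.

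The rule is also robust. It tolerates the loss of up to 100 of the 350 positives, and precision worsens only modestly until the loss is large. That stands too.

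Section 5 says that a treatment paradox will not affect Analyses 1 to 3. That concerns agreement between paired readings, not how many women are positive. The Group C text expects few exclusions for early treatment, but it says so of the multivariate analysis. The broader sentence covers all the analyses and conflicts with Analysis 1.

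A reader might infer that the stated interval will not be achieved, using the 4.1% reduction with compression garments reported in section 1.4 to estimate how many women revert. The documents do not support this. Those women were identified at swelling of 3% or more, wore garments for a mean of 4.4 weeks and were followed for 4.8 months on average. They were not women with lymphoedema above 10% read at 18 months.

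**Conclusion.** The point holds as a gap in the justification, not as a demonstrated loss of precision. Analysis 2 is defined on status at a visit. Its 350 positives read as women who have developed lymphoedema by then, with no allowance for treatment, and section 5 gives two incompatible statements on whether early-treated women are used.

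The size is unknown because no reversion rate is given. The 92% line is safe for 250 to 350 positives and unreliable at 249 or fewer. False rejection of a true 95% sensitivity is 3.6% at 210 and 4.9% at 140, against a nominal 2.5%. The ±5% promise is missed only slightly, at about 140. Specificity is not threatened.

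The statement that later analyses rest on larger numbers may still be true for Analysis 2, so it needs a condition rather than removal. Nor should a reader conclude that 350 remains the right count for the Cox model: Analysis 4 excludes women who develop lymphoedema before 6 months.

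**What to change.** In section 5:

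1. State whether the 35% is cumulative incidence by 18 months or prevalence at the 18-month visit, and define the Analysis 2 positives as perometer status at that visit.
2. Reconcile Analysis 1, which keeps treated cases, with the later statement that no analysis uses cases treated before 6 months. Say which applies to Analysis 2.
3. Show the exact interval over a labelled range of positives, for example 140 to 350, in place of the single figure.
4. Replace the fixed 92% line with this rule: conclude that sensitivity is below 95% if the exact upper 95% limit, at the observed number of positives, is below 95%.
5. Qualify the Sample Size Calculation statement on larger later numbers, so that for Analysis 2 it depends on how many women still read above 10% at 18 months.

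The cost is a wording change. No extra patients or visits are needed, though the precision shown at the low end of the range is less favourable.
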